Treatment of tumors in the paranasal region often necessitates either palatal maxillectomy or radical maxillectomy. Surgical and prosthetic interventions offer avenues to treat post-maxillectomy patients, ensuring both functional and aesthetic outcomes. However, despite the advantages associated with surgical procedures, reconstructive surgery may not always be feasible due to the patient's overall health condition and the extent of the defect. In such cases, prosthetic reconstruction becomes imperative. ⁽¹⁾

Temporary or permanent obturators serve as effective solutions in prosthetic reconstruction, aiming to separate the oral and sinonasal cavities, thus preventing issues like hypernasal speech and fluid leakage into the nasal cavity. These prosthetic devices also play a pivotal role in restoring functions such as chewing, swallowing, and speech, while providing support to the lips and cheeks, thereby aiding in the restoration of facial contour. Moreover, they contribute significantly to alleviating the social and psychological distress experienced by patients. ⁽²⁾

The emergence of rapid prototype production technology, also known as rapid prototyping (RP) or laser-layered manufacturing, has revolutionized the creation of three-dimensional solid models. This technique, which has seen global advancement since 1995, enables the layer-by-layer production of physical models directly from computer-aided designs in a single step. Unlike traditional computer-assisted design (CAD)-computer-aided manufacturing (CAM) systems that involve material removal, rapid prototype techniques employ technologies like lasers and numerical control to build models layer by layer, facilitating the creation of intricate internal details and smooth surfaces, even in complex structures. ⁽³⁾

Various rapid prototype techniques, including stereolithography (SLA), laminated object manufacturing, selective laser sintering, fused deposition modeling, and three-dimensional printing, offer diverse options for model production. These techniques, which utilize different materials and layering methods, can be combined to achieve desired outcomes. ⁽⁴⁾

Rapid prototype production techniques present a viable alternative to conventional methods for constructing facial prostheses. By utilizing computer-aided imaging techniques such as computed tomography (CT), magnetic resonance imaging (MRI), and laser surface scanners, highly accurate extraoral facial prostheses can be crafted using CAD–CAM and RP technologies, ensuring excellent contours and tissue adaptation. ⁽⁵⁾

While conventional gypsum models are typically used for prosthetic rehabilitation of intraoral deformities like maxillectomy defects, the integration of 3D CAD and RP technologies can significantly enhance outcomes. A crucial aspect of creating a functional and aesthetically pleasing prosthesis lies in obtaining an accurate impression. Factors such as the properties of the

impression material, the size and nature of the defect, the presence of undercuts, and the condition of remaining teeth influence the accuracy of the impression. Challenges such as pain, tears, and deformations during impression removal, as well as bleeding and mucosal adhesion, further complicate the process. Additionally, limitations in mouth opening may hinder optimal insertion of the impression materials. ⁽⁶⁾

Aim of the Study

Research Question

In patients with maxillary defects, which type of denture base materials fulfill accuracy parameters regarding extent of the maxillary defect?

Research Hypotheses

There is no difference between different denture base materials of maxillary obturator regarding bulb accuracy over the extent of maxillary defect.

Outcomes

- Accuracy, measuring device: metrology software (Geomagic Control X 20, 3D Systems, Rock Hill, SC, USA).
- 2. Patient satisfaction using Obturator Functional Scale (OFS).

Materials and Methods

Study Settings

Randomized controlled study. Patients will be selected and diagnosed by the investigators to be enrolled in the trial from the outpatient clinic of faculty of Oral and Dental Medicine, Badr University in Cairo.

Eligibility Criteria

Inclusion Criteria

- The study included participants of both male and female genders.
- The patients had defects or abnormalities in both the hard and soft portions of their palate.

- The surgical wound or site had to be fully healed.
- The upper jaw (maxilla) had partial tooth loss or missing teeth in the defect.
- Cooperative patients who could follow instructions were selected for the study.

Exclusion Criteria

- Temporomandibular disorders
- Uncontrolled diabetes
- Bleeding disorders or anticoagulant therapy
- Flabby tissues or sharp mandibular residual ridge.
- Heavy smokers.
- Patient's with neuromuscular disorders
- Severe psychiatric disorders
- Children were not included in the study; only adult participants were considered.

Justifying Exclusion Criteria

Temporomandibular disorders (TMD) that could affect the direction of force applied on the dentures were exclusion criteria, as TMD symptoms may mask or influence the expected improvement and patient satisfaction with the overdentures.

Patients with severe systemic diseases like uncontrolled diabetes, bleeding disorders, neuromuscular disorders, psychiatric conditions, or those undergoing chemotherapy or radiotherapy were excluded. Management of their conditions requires special considerations like adjusted medication doses, shorter appointment times preferably in the morning, and they have a higher risk of dropping out during the trial follow-up period.

Patients presenting with flabby tissues or sharp/undercut mandibular residual ridges were excluded as they require modified impression techniques like sectional trays and plaster materials for flabby tissues. Frequent tissue conditioning is also necessary throughout follow-up, which could confound the trial results.

Heavy smokers were excluded as smoking can compromise the physical retention of complete dentures, which relies on surface tension and a thin salivary film between the denture and tissues for capillary attraction. Smoking decreases salivary flow causing dry mouth

(xerostomia), which jeopardizes denture retention. Additionally, smoking may affect the long-term success of implant osteointegration.

Interventions

A perforated stock tray underwent modifications including reduction, bending, or addition of modeling wax to accurately capture the entire defect. Undesirable undercuts in the defect were blocked using vaselinized gauze. Preliminary impressions were taken with irreversible hydrocolloid material, extending into the surgical cavity to replicate undercuts as closely as possible. Mandibular impressions were also made with alginate. After verifying details, impressions were poured to obtain diagnostic casts. These casts were surveyed to identify survey lines, guiding planes, and undercut depths, informing path of insertion selection. Mouth preparation followed, with guiding planes prepared on abutment distal surfaces and palatal tooth surfaces modified for proper reciprocal clasp positioning. Final impressions were taken using a special tray, with modeling wax border molding at the surgical site. After setting, impressions were boxed and poured to create master casts. Refractory casts and wax patterns were crafted for obturator framework planning, ensuring retention, stability, support, and reciprocation. Metal framework try-in was conducted to confirm accuracy before proceeding with acrylic resin application. Jaw relation registration was performed using the wax wafer technique.

Groups Design:

Group I: received maxillary obturators constructed with hard acrylic applied on the posterior part of the obturator.

Group II: received maxillary obturators constructed with injection-molded PMMA resin.

Sample Size Calculation and Statistical Analysis

Based on *Abdelfattah Mohamed A, kothayer Marwa 2020*, we are planning a study of independent cases and controls with 1 control(s) per case. Prior data indicate that the probability of exposure among controls is 0.2. If the true probability of exposure among cases is 0.6, we will need to study 22 cases in each group to be able to reject the null hypothesis that the exposure rates for case and controls are equal with probability (power) 0.8. The Type I error probability associated with this test of this null hypothesis is 0.05. We will use an uncorrected chi-squared statistic to evaluate this null hypothesis. Data will be analysed using IBM SPSS advanced statistics

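### Do the unmatched descriptions of the two arms stop the trial from answering a question about denture base materials?

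*Protocol*

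**What the plan says.** Under Research Question, the protocol asks "which type of denture base materials fulfill accuracy parameters regarding extent of the maxillary defect". Research Hypotheses gives the matching null: "There is no difference between different denture base materials of maxillary obturator regarding bulb accuracy", taken over the extent of the defect. Under Interventions, impressions, casts, mouth preparation, framework and jaw registration are described once, for all patients. Framework try-in takes place "before proceeding with acrylic resin application", and nothing further is said about that resin step. Groups Design then separates the arms. Group I's obturators are "constructed with hard acrylic applied on the posterior part of the obturator"; Group II's are "constructed with injection-molded PMMA resin". The study is described as randomized and controlled.

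**The concern.** Each arm names a material, but the added qualifier is of a different kind in each: a location for Group I, a manufacturing method for Group II. The shared text does not say that processing and location are common to both arms. Randomization balances the patients. It cannot separate material from another feature that is built into one arm.

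If the arms did differ in processing or in where the resin is placed, a difference in bulb accuracy could arise from any of the three features. A conclusion about material would then claim more than the design supports. The outcome concerns the bulb, so location might matter in particular. The introductory background also links manufacturing technology with good fit, which seems to make production method a rival explanation on the protocol's own terms.

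**Working it through.** No plan figure bears directly on this point, so the check sets the texts side by side.

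**1. What each arm's description states**

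| Attribute | Group I | Group II |
|---|---|---|
| Material | hard acrylic | PMMA resin |
| Processing | not stated | injection-molded |
| Site | posterior part of the obturator | not stated |

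The two empty cells are silences. Neither conflicts with anything else in the protocol. Nothing places Group II's resin somewhere other than Group I's, and nothing says how Group I's resin was processed. Counting filled and empty cells does not measure bias, because the choice of attributes is the reader's own.

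**2. Whether question and arms are compatible**

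The question asks about types of denture base material, and Groups Design names two. A processed resin can reasonably be called a type of base material, and the question does not exclude processing from that term. The site wording for Group I may simply point to the bulb region, where the outcome is measured. That is a possible reading, not a proven one. Under these readings the two sections agree.

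**3. Whether the background makes processing a rival explanation**

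The phrase "RP technologies, ensuring excellent contours and tissue adaptation" describes facial prostheses worn outside the mouth and made from imaging data. The statement that "the integration of 3D CAD and RP technologies can significantly enhance outcomes" sets digital design and rapid prototyping against plaster models. Neither concerns how acrylic or PMMA is processed on a master cast, and Interventions describes no digital or prototyping step for either arm. The accuracy factor that the background does stress for intraoral work is the impression, and that procedure is common to both arms. The protocol therefore offers no argument of its own that resin processing alters bulb accuracy.

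**4. Whether any number moves**

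The only design figure is 22 per group, from proportions 0.2 and 0.6, two-sided alpha 0.05, power 0.8 and an uncorrected chi-squared test. With mean proportion (0.2 + 0.6)/2 = 0.4:

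n = [1.960·√(2·0.4·0.6) + 0.842·√(0.2·0.8 + 0.6·0.4)]² / (0.6 − 0.2)² = 22.33

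This is close to the stated 22, and power at 22 is 79.4%. No term in the formula depends on whether the contrast is called one of materials or of constructions. Whether that calculation suits the outcome is a separate matter. The between-arm estimate and its test are likewise the same under either label.

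**5. Whether rewording would help**

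A hypothesis about obturators made as in Group I against those made as in Group II points back to the same two incomplete descriptions. The reader would know no more about the arms. The protocol also contains no planned-conclusion text that could be narrowed.

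**The case for a change.** The strongest case for a change is that defining the interventions belongs in the protocol and cannot be left to the SAP. The shared text mentions a single acrylic resin step without limiting it to one arm. If both arms receive an acrylic resin, the clearest distinguishing terms are a process and a site, and neither is a material. If materials were equivalent and processing mattered, the test would reject the hypothesis as worded for a reason other than material. A sentence in the protocol would cost nothing.

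Part of this stands. The descriptions are not parallel, the document does not say that the unstated attributes are shared, and randomization would not separate them if they differed. But the argument is conditional on a difference that the document neither states nor implies for site, and leaves open for processing. It shows incomplete description, not a wrong rule or a contradiction. What it protects is the wording of a conclusion. The comparison of the two constructions as delivered is valid either way.

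**Conclusion.** No change to the plan is needed. The arm descriptions are uneven, but they are compatible with the question and hypothesis. The effect on the randomized comparison, its test and its sample size is nil. The possible misattribution cannot be sized, because the documents give no figure for the effect of processing or site on accuracy.

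This rests on two assumptions: that a type of denture base material may include the form in which it is processed, and that the investigators will record material, processing and site for both arms when they report what was delivered. If that record shows a difference beyond material, the result should be described as a comparison of two constructions. That is a matter of careful reporting and can be settled without altering the design or the analysis.

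### The 22 per group and the 0.8 power are worked out for an undefined yes/no exposure, not for bulb accuracy, which is the hypothesis under test

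*Protocol*

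**What the plan says.** Under Study Settings the protocol calls the trial a "Randomized controlled study". Under Research Hypotheses it states one null hypothesis: "There is no difference between different denture base materials of maxillary obturator regarding bulb accuracy over the extent of maxillary defect". Under Outcomes it lists two measures: "Accuracy, measuring device: metrology software" and "Patient satisfaction using Obturator Functional Scale (OFS". No cut-off, pass/fail rule or responder definition is given for either.

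The section Sample Size Calculation and Statistical Analysis uses different terms. It says "we are planning a study of independent cases and controls with 1 control(s) per case", then "Prior data indicate that the probability of exposure among controls is 0.2", then "If the true probability of exposure among cases is 0.6, we will need to study 22 cases in each group", for power 0.8 at a type I error of 0.05. The test is named: "We will use an uncorrected chi-squared statistic to evaluate this null hypothesis". The rates are attributed to a 2020 study which, by its title in the reference list, concerns quality of life with a maxillary obturator.

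The same section then assigns numeric variables to ANOVA or Kruskal-Wallis, and categorical data to chi-square or Fisher's exact test. All tests are two-tailed.

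**The concern.** A power figure belongs to one endpoint, one effect size and one test. The null hypothesis that is powered here (equal exposure rates) is not the one the trial states (no difference in bulb accuracy). Exposure is not defined anywhere in the protocol, and no difference or SD is given for accuracy or for the OFS.

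The case-control vocabulary is not itself the fault, since the arithmetic for two independent proportions is the same in a randomised trial. The fault is that the endpoint and effect size behind the 22 are not those of the hypothesis.

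What is at stake is how a non-significant accuracy result is read. A confidence interval would still be informative, but the protocol does not say what difference in bulb accuracy the trial was sized to detect, or what difference would matter. A reader could not tell similar materials from a trial unable to separate them.

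**Working it through.** **1. Reproducing the stated figure.** Inputs from the sample size section: p1 = 0.2, p2 = 0.6, two-sided α = 0.05, power 0.8, 1:1 allocation, uncorrected chi-squared. The mean proportion is 0.4.

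n per group = [z(0.975)·√(2·p̄(1−p̄)) + z(0.8)·√(p1(1−p1) + p2(1−p2))]² / (p2−p1)²

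= [1.960·√0.48 + 0.842·√0.40]² / 0.16 = (1.358 + 0.532)² / 0.16 = 22.3

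Exact power of the uncorrected chi-squared test, by enumerating both binomials, is 79.1% at 22 per group and 81.9% at 23. Strict rounding up would give 23, but the stated 22 and 0.8 are reproduced closely enough. The sum is right for its inputs.

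**2. Looking for the endpoint.** To carry the 0.8 over to the hypothesis, 0.2 and 0.6 must be rates of something measured in the trial.

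- Accuracy: an instrument is named, but no threshold.
- OFS: a scale is named, but no responder rule.
- Any other binary outcome: none is listed.

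That leaves two readings. If accuracy is numeric, the protocol's own plan is ANOVA or Kruskal-Wallis, to which a power figure for 0.2 versus 0.6 does not apply. If accuracy is pass/fail, the criterion is missing and the two rates have no stated meaning.

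**3. What 22 per group can detect on a numeric measure.** The protocol gives no difference or SD, so the standardised differences d below are assumptions. The comparison is of two group means, two-sided 5%, 42 degrees of freedom, non-centrality d·√(22/2). With two groups, one-way ANOVA gives F = t², so the same figures hold for ANOVA applied to the two groups that the protocol describes.

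| Assumed d (SD) | Power at 22 per group | n per group for 80% power |
|---|---|---|
| 0.3 | 16% | 176 |
| 0.5 | 37% | 64 |
| 0.8 | 74% | 26 |
| 0.865 | 80% | 22 |
| 1.0 | 90% | 17 |

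**4. Precision.** The half-width of the 95% confidence interval for the difference is t(0.975, 42)·√(2/22) = 2.018 × 0.3015 = 0.61 SD.

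**The case against.** The strongest reply is that the link may exist without being spelled out. The rates come from a cited study whose title concerns quality of life with an obturator, which is close to the second outcome, satisfaction by the OFS. The research question asks which material fulfils accuracy parameters, which can be read as pass/fail, and the analysis section does plan chi-square tests for categorical data. All of this is in the text, and it shows that a binary endpoint may have been intended. It does not say which one. The protocol does not equate exposure with an OFS response or an accuracy pass, and a quality-of-life source, taken at its title, would not supply rates for bulb accuracy. A separate SAP could add analysis detail, but the protocol itself has already fixed the sample size on an endpoint missing from its outcome list.

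It is also fair to say that no shortfall has been shown. The 16% to 90% range reflects assumed effects only, so the supportable word is unjustified, not underpowered.

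Some reservations about the repair stand as caveats on the 0.865 SD:

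- It is solved backwards from 22, so it becomes a justification only once a reason is given why a difference of that size matters.
- The protocol's rank test would have slightly less power (about 78% at 0.865 SD under normality, by simulation).
- Dropout would lower it: about 76% with 20 analysed per group and about 71% with 18, both assumed numbers.
- The analysis text speaks of three groups where two are described. If three were meant, with Bonferroni-adjusted pairwise tests (an assumption), power at 0.865 SD would be about 65%.

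None of these rescues the existing paragraph.

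**Conclusion.** The concern holds, and the paragraph is wrong as written. The 22 per group is correctly calculated for a 0.2 versus 0.6 binary contrast, but that contrast is not tied to either listed outcome, so the claimed 0.8 is not established for the bulb accuracy hypothesis. On a numeric reading, with two groups, roughly normal data and all 22 per group analysed, the trial has 80% power only for a difference of about 0.865 SD. Whether that is adequate cannot be judged from the protocol. This must be fixed: it is the only justification given for the trial's size, and it does not bear on the only hypothesis.

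**What to change.** Delete the case-control and exposure wording, keep 22 per group, and replace the calculation with a statement such as:

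> With 22 patients per group, a two-sided 5% comparison of the two groups (two-group ANOVA, equivalent to a two-sample t-test) has about 80% power to detect a difference of 0.865 SD in bulb accuracy.

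Then convert 0.865 SD into the units of the accuracy measure, using an SD from accuracy data, and say why a difference of that size matters. State that the figure assumes 22 analysed per group, and bring the three-group wording of the analysis text into line with the two groups described.

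If a binary accuracy criterion was intended, define it, justify 0.2 and 0.6 for that criterion, and make its chi-squared test the primary analysis.

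The cost is one paragraph and no extra patients. The drawback is that the detectable difference is then openly large. If a smaller one matters, 80% power would need 26 per group at 0.8 SD or 64 per group at 0.5 SD, before any allowance for dropout.
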